Standard vs Ultrasound-assisted Catheter Thrombolysis for Submassive Pulmonary Embolism NCT03086317

Date: February 10, 2017 IRB number: 00093040

Standard vs Ultrasound-assisted Catheter Thrombolysis for Submassive Pulmonary Embolism

Principal Investigators: [name] and [name]

IRB number: 93040

Draft date: February 10, 2017

SUMMARY

Background: Acute pulmonary embolism (PE) accounts for 5-10% of in-hospital deaths. Systemic anticoagulation (AC) is the standard of care and thrombolysis is recommended for those at a higher mortality risk. Catheter-directed therapies mainly standard catheter thrombolysis (CDT) and ultrasound-accelerated thrombolysis (USAT) have been introduced as new more effective and safer treatment modalities. USAT is a modification of standard catheter lysis utilizing a system of local ultrasound to dissociate the fibrin matrix of the thrombus, allowing deeper penetration of lytics. However, there is limited comparative effectiveness data against standard multi-sidehole catheter infusion. More rapid clearance of pulmonary thrombus by USAT compared to standard CDT may prove to be clinically and cost effective. Alternatively, if thrombus clearance is similar, the cost of USAT may exceed the cost of CDT (equipment and disposables), without offering any potential advantage.

Hypothesis: Ultrasound Accelerated Thrombolysis is superior to Standard Catheter Thrombolysis for patients with submassive PE

Objectives/Aims: 1. Determine differences in the percentage of thrombus load reduction (CTA Obstruction Index) from baseline to the termination of lysis; 2. Determine differences in cardiopulmonary and clinical outcomes; **3.** Determine differences in the impact of catheter directed intervention on functional capacity (NYHA score and 6-min walk test) and health-related quality of life outcomes (SF36, PE QOL, and San Diego Shortness of Breath questionnaires at 3 and 12 months; 4. Detail the cost differences in hospital resource utilization (i.e., procedure costs, adverse event costs, and hospital stay) and discharge costs (nursing care, subsequent outpatient care) to inform a Markov state-transition cost-effectiveness model.

Design: Randomized controlled trial.

Statistical Power: The study is powered on the primary endpoint. 40 patients will be needed at each group for a power of 0.80.

RESEARCH PLAN

a. SPECIFIC AIMS

- **Hypothesis:** Ultrasound Accelerated Thrombolysis is superior to Standard Catheter Thrombolysis for patients with submassive PE
- Aim 1: Determine differences in the percentage of thrombus load reduction from baseline to the termination of lysis between the two techniques
- Aim 2: Determine differences in cardiopulmonary (echocardiographic, hemodynamic and respiratory parameters) and clinical outcomes (decompensation, mortality, complications, ICU stay) between the two techniques
- **Aim 3:** Determine differences in the impact of catheter directed interventions on functional capacity and health-related quality of life outcomes at 3 and 12 months
- Aim 4: Perform a cost effectiveness analysis to compare quality adjust life years and costs of the two techniques.

b. BACKGROUND AND SIGNIFICANCE

Acute pulmonary embolism (PE) carries a high morbidity and is the third-leading cause of cardiovascular mortality in the western world. It accounts for 5-10% of in-hospital deaths that for the United States translates to 200,000 deaths per year.¹ Recent registries and cohort studies suggest that approximately 10% of all patients with acute PE die during the first 1 to 3 months after diagnosis.¹⁻⁵ Studies that have observed survivors for >3 months have reported an incidence of chronic thromboembolic pulmonary hypertension (CTEPH) 1-5% within 2-3 years after PE.⁶⁻¹⁰ It is an incapacitating long-term complication of thromboembolic disease with a negative impact on the patient's quality of life and prognosis.

The management acute PE is mainly guided by the acuity and severity of clinical presentation. Initial systemic anticoagulation (AC) is the standard of care and treatment is escalated based on the clinical presentation and patient characteristics that may stratify them at a higher mortality risk. The goals of therapy are to primarily prevent mortality, and secondarily potentially prevent late onset chronic thromboembolic pulmonary hypertension (CTEPH) and improve quality of life.^{2, 3, 5, 11-14}

Massive PE is defined as PE associated with sustained hemodynamic instability, whereas submassive PE (sPE) is defined as PE without hemodynamic instability but with abnormal right ventricular (RV) function and/or evidence of myocardial necrosis.³ It is notable that there is ongoing interest to accurately risk stratify sPE to identify the patients who are at increased risk of decompensating and/or dying. Clinical scores, imaging tests and biomarkers are under investigation, yet an ideal prognostic tool is still pending. A novel cardiac biomarker, heart-type fatty acid-binding protein (h-FABP), is emerging as a significant predictor of mortality in patients with submassive PE.^{15, 16}

Systemic intravenous thrombolysis is universally recommended by all guideline bodies for massive pulmonary embolism, but remains controversial for submassive PE.^{3-5, 17} In the most recent metaanalysis, the subgroup analysis of 8 submassive PE trials (1993-2014, n=1775)

showed that thrombolytic therapy was associated with a mortality reduction (1.39% vs 2.92%) but with an increase in major bleeding (7.74% vs 2.25%).¹¹ These results were mainly driven by the largest randomized trial (PEITHO, 1006 patients) which compared a single, weight-adapted i.v. bolus of tenecteplase with standard anticoagulation.¹⁸

The recent development of catheter-directed therapies such as catheter-directed thrombolysis (CDT), ultrasound-accelerated thrombolysis (USAT), and pharmacomechanical or aspiration thrombectomy has introduced more tools for the treatment of acute PE.² Proponents of these techniques suggest that they may provide a similar therapeutic benefit as systemic thrombolysis, while decreasing the dose of thrombolytic required and potentially decreasing the risk of adverse bleeding events.¹⁹⁻²⁴ Both the American Heart Association and more recently European Society of Cardiology have acknowledged CDT as a viable treatment alternative for high risk acute sPE (echocardiographic RV dysfunction and elevated cardiac biomarkers), if appropriate expertise is available and particularly when the bleeding risk is high.^{3, 5}

Catheter-directed thrombolysis requires placement of a multi-sidehole infusion catheter within the pulmonary arterial thrombus burden under angiographic guidance. Thrombolytic medications are slowly infused through the catheter, which is left in place for the duration of the treatment. USAT is a modification of this therapy utilizing a proprietary system of local high frequency, low-power ultrasound to dissociate the fibrin matrix of the thrombus, allowing deeper penetration of lytic medication.

Several observational non-controlled series have demonstrated the efficacy of catheterdirected techniques in improving clinical and hemodynamic parameters and reducing clot burden while demonstrating a favorable safety profile.^{2, 19, 23, 25-28} The ULTIMA trial was the first randomized controlled trial to include CDIs for sPE comparing standardized fixed-dose of USAT (10mg rtPA per lung over 15 hours) and AC to AC alone.²¹ In the USAT group, but not in the heparin group, the mean RV/LV ratio was significantly reduced at 24 hours, but became comparable between the two groups at 90 days. The RV systolic function was significantly improved in the USAT group vs. the heparin group at both 24 hours and 90 days. In both study groups minor bleeding complications were rare and there were no major bleeding complications. The SEATTLE II trial, a single-arm study evaluating the effectiveness of USAT, showed also an RV/LV ratio improvement at 48 hours.²⁹

Limited data exists for comparing different catheter-directed therapies for acute PE. The majority of recent series for catheter-directed interventions utilize USAT exclusively; however there is limited comparative effectiveness data comparing this modality to standard multi-sidehole catheter infusion.^{15, 16, 19, 30} Preliminary, non-controlled data are conflicting. One series by Lin and colleagues of 33 high-risk PE patients suggested benefit for USAT for angiographic clearance of thrombus burden with more bleeding events in the CDT group.³¹ Kuo and colleagues noted no difference in outcomes and treatment specifics between USAT and CDT in the recently published early results of a multicenter prospective registry.²⁸ Our retrospective analysis of 63 patients suggests that there may be no difference between the two treatment modalities, demonstrating similar rates of outcomes such as survival, hemodynamic stabilization, and echocardiographic parameters in both groups with similar procedure length and lytic dose in the time-adjusted cohorts.³² Selection bias cannot be underestimated in all these studies.

The expected benefit of USAT has been dependent on the device's ability to increase penetration of lytic into thrombus using high frequency, low power ultrasound, due to its reversible effects on fibrin dissociation.^{19, 21} This benefit has been shown to result in faster thrombus clearance in selected vascular beds in some studies, such as the recently published DUET study comparing USAT and CDT in arterial occlusions.³³ Evidence from the venous circulation, coming

from the recent BERNUTIFUL trial demonstrated no difference in time to thrombus clearance in lower extremity deep venous thrombosis.³⁴

c. INNOVATION

There are no randomized controlled studies that have compared the outcomes of catheter directed thrombolysis with and without ultrasound acceleration. More rapid clearance of pulmonary thrombus by USAT compared to standard CDT may prove to be clinically and cost effective (e.g. via reduced length of ICU and hospital stay). Alternatively, if thrombus clearance is similar, the cost of USAT may exceed the cost of CDT (proprietary equipment and disposables), without offering any potential advantage.

Preliminary, non-controlled data are conflicting. One series by Lin and colleagues of 33 highrisk PE patients suggested benefit for USAT for angiographic clearance of thrombus burden with more bleeding events in the CDT group.³¹ Kuo and colleagues noted no difference in outcomes and treatment specifics between USAT and CDT in the recently published early results of a multicenter prospective registry.²⁸ Our retrospective analysis of 63 patients suggests that there may be no difference between the two treatment modalities, demonstrating similar rates of outcomes such as survival, hemodynamic stabilization, and echocardiographic parameters in both groups with similar procedure length and lytic dose in the time-adjusted cohorts.³² Selection bias cannot be underestimated in all these studies.

A controlled randomized study will better determine if ultrasound acceleration adds any benefits in the outcomes and costs of catheter directed thrombolysis for patients with acute submassive PE.

d. APPROACH

The study will be designed as a randomized controlled trial comparing standard catheter directed thrombolysis to ultrasound accelerated thrombolysis for the treatment of acute submassive PE.

The study will include patients eligible for catheter directed thrombolysis per the study protocol for submassive PE (CT or echocardiographic RV strain (defined as RV/LV ratio >1) without persisting hypotension <90mmHg or drop of systolic blood pressure by at least 40mm Hg for at least 15 minutes with signs of end-organ hypoperfusion (cold extremities or low urinary output <30 mL/h or mental confusion) and without the need of catecholamine support or cardiopulmonary resuscitation).

The treatment with CDT or USAT are standard of care for submassive PE. All the procedures, tests and follow up visits are according to current standard of care.

Exclusion criteria: age <18; pregnancy; index PE symptom duration >14 days; high bleeding risk (any prior intracranial hemorrhage, known structural intracranial cerebrovascular disease or neoplasm, ischemic stroke within 3 months, suspected aortic dissection, active bleeding or bleeding diathesis, recent spinal or cranial/brain surgery, recent closed-head or facial trauma with bony fracture or brain injury); participation in any other investigational drug or device study; life expectancy <90 days; and inability to comply with study assessments.

At baseline all patients need to have

- 1. Chest CT angiogram with contrast diagnostic of PE
- 2. Baseline transthoracic echocardiogram
- 3. Baseline cardiac biomarkers
 - a. Cardiac troponin (cTn)
 - b. Brain Natriuretic Peptide (BNP) and/or N-terminal pro-BNP (NT-proBNP)

All patients will be treated initially with unfractionated heparin by using a standardized dosing protocol. Immediately after consent, vital signs will be recorded, a pulse oximetry reading will be obtained with the patient breathing room air for 2 min.

All eligible patients will undergo catheter-directed thrombolysis randomized to either a standard commercially available multi-sidehole catheter or a USAT catheter.

Technical considerations (access, intraoperative tPA bolus, tPA dripping dose etc) will be left to the discretion and preference of the operator. Invasive pressure tracings will be obtained from the drug delivery catheters when positioned in the pulmonary arteries (main, right or left). The maximum tPA dosing should not exceed 24mg.

Termination of lysis will be left to the discretion of the operator. As a general recommendation lysis should be terminated once clinical (e.g. O2 requirements), hemodynamic (e.g. pulse rate or blood pressure) and/or echocardiographic parameters (e.g. RV dilatation) improve or if a complication occurs. Lysis catheters and sheaths can be removed at the bedside. Before removal, invasive pressure tracings will be recorded from the drug delivery catheter.

A transthoracic echocardiogram should be obtained just before or within 24 hours after the termination of lysis.

Within 48h after the termination of lysis patients will get a chest CTA examination.

Patients will be followed up at 3 months and 12 months.

Primary Endpoint: PE thrombus load reduction (CT obstruction index) from baseline to the termination of lysis.

The pre and post lysis CTA will be compared by 2 blinded independent radiologists. For determining the CT obstruction index, the arterial tree of each lung will be considered to have 10 segmental arteries (three to the upper lobes, two to both the middle lobe and the lingula, and five to the lower lobes). The vascular obstruction scores will be determined as previously described by Qanadli et al. and Mastora et al.^{35,36}

Secondary Endpoints:

- 1. Clinical outcomes comparison
 - a. In hospital and 90-day mortality
 - b. Decompensation to massive PE (hypotension <90mmHg and use of catecholamines)
 - c. Major and minor bleeding. Major bleeding is defined as overt bleeding associated with a fall in the hemoglobin level of at least 2.0 g/dL or with transfusion of ≥2 U of red blood cells or involvement of a critical site (intracranial, intraspi-nal, intraocular, retroperitoneal, intra-articular or pericardial, or intra-muscular with compartment

syndrome). Clinically overt bleeding not fulfilling the criteria of major bleeding is classified as a minor bleeding complication.

- d. Recurrent venous thromboembolism (VTE) during 90-day follow-up. There will be no routine surveillance for asymptomatic recurrent VTE. Recurrent VTE will be diagnosed if suspected symptoms or signs of deep vein thrombosis or acute PE are objectively confirmed by an imaging test (new filling defect by pulmonary angiography or contrast-enhanced chest CT, new high-probability perfusion defect revealed by lung scan, or positive compression ultrasound study for deep vein thrombosis).
- e. Major adverse events up to 90 days after randomization.
- f. Clinical success: PE related decompensation prevention without a 90-day major adverse event or death.
- g. ICU length of stay
- 2. Echocardiographic parameters comparison
 - RV/LV, TAPSE (Tricuspid annular plane systolic excursion) and RVSP (Right Ventricular Systolic Pressure) improvement from baseline to the termination of lysis
 - b. RV/LV, TAPSE and RVSP at 90 days
 - c. RV/LV, TAPSE and RVSP at 12 months

The echocardiograms will be interpreted by 2 blinded independent cardiologists.

3. Functional status and quality of life

At the 3 and 12-month follow-up visit, patients will complete a written survey to assess the NYHA score and answer other questions about functional status. Patients will then perform a 6-minute walk test according to published guidelines.^{37,38}Transthoracic echocardiography will be also performed as described earlier.

Quality of life will be assessed at 3 and 12 months using SF36, PE QOL, and San Diego Shortness of Breath questionnaires.

4. Cost effectiveness analysis

A Markov state-transition, cost effectiveness model will be created to simulate patient oriented outcomes assuming a societal perspective with a 12-month time horizon. All point estimates for model parameters will be determined from the prospectively collected data, as described above. Quality adjusted life years will be determined for each therapy based on survival, freedom from major adverse events, discharge status, functional status, and quality of life measures. Costs will be calculated for each therapy based on in-hospital resource utilization (i.e., length of stay in the ICU, operating room and procedure costs, and associated adverse event costs) and out-of-hospital costs (outpatient nursing care, loss of work, outpatient testing and follow-up).

Schedule of Events

			Randomization US assisted or standard		Prior to Lysis Termination	Within	3month f-up	12month f-up
	Deceline	Correction	catheter	Lysis	or within 24h	48hrs	+/-14	+/- 30
	Baseline	Screening	thrombolysis	Procedure	post lysis	post lysis	days	days
Informed Concept		V						
	X	X				N N		
Chest CTA	X					X		
Transthoracic								
Echocardiogram	X				X		X	X
Cardiac troponin	×							
Drain Natriuratia								+
Brain Natriuretic	v							
	^							
N-terminal pro-								
BNP(NI-proBNP)	X							
IV Unfractionated								
Heparin		X						-
Vital Signs		X						
2min Pulse Ox		X						
Ultrasound								
Catheter Placement			Х	Х				
Standard Catheter								
placement			X	X				
Invasive Pressure								
Tracings from drug								
delivery catheter				X(a)	X(b)			
Functional Status								
NYHA							X	X
Quality of Life								
Questionnaires							X	X
Six Minute Walk Test							x	x

(a) Before lytics administered

(b) After lytics administered

Statistical Analysis:

The study is powered on the primary endpoint that is thrombus load reduction (obstruction index). We propose to compare standard CDT and USAT at post-treatment with analysis of covariance, controlling for differences remaining after randomization. Population parameters for the obstruction score have not been published, so we consulted several relevant studies reporting on thrombus reduction scores in order to predict sample size.^{19,31,34,39} We assumed that CDT with ultrasound enhancement (USAT group) should be \geq 50% more effective than without ultrasound enhancement (control group) and calculated an expected relative mean thrombus reduction of 43% in the CDT control group.^{40,41} We estimated a sample size of 40 per group to detect the differences with a power of 0.80.

REFERENCES

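### Does an operator-chosen end of lysis, with infusion time and total tPA not listed as outcomes, undermine the primary comparison?

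*Combined protocol and SAP*

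**What the plan says.** Section d (APPROACH) defines the outcome as "Primary Endpoint: PE thrombus load reduction (CT obstruction index) from baseline to the termination of lysis". Aim 1 in section a is worded to match: "Determine differences in the percentage of thrombus load reduction from baseline to the termination of lysis between the two techniques".

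The end point in time is not fixed: "Termination of lysis will be left to the discretion of the operator". A general recommendation follows, to stop on clinical, hemodynamic and/or echocardiographic improvement or on a complication. Dosing is equally free, "Technical considerations (access, intraoperative tPA bolus, tPA dripping dose etc) will be left to the discretion and preference of the operator", subject to one limit: "The maximum tPA dosing should not exceed 24mg". The post-lysis CTA is taken within 48 hours of stopping.

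The secondary endpoints include bleeding and ICU length of stay. Objective 4 in the SUMMARY adds hospital stay and procedure costs. Neither infusion duration nor total tPA appears among the endpoints, in the Schedule of Events or under Statistical Analysis.

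Section c (INNOVATION) gives the motive: "More rapid clearance of pulmonary thrombus by USAT compared to standard CDT may prove to be clinically and cost effective". In that section the sentence goes on to give shorter ICU and hospital stay as the example of how this would come about. It then notes that, if clearance proves similar, ultrasound may only add cost.

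**The concern.** The case for ultrasound is put partly in terms of speed, but the endpoint measures extent at a moment that each operator picks in response to how the patient is doing. Blinding is described for the radiologists and cardiologists who read the images, not for the operators. The dose cap limits exposure in both arms without making it equal.

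If the ultrasound catheter works faster, its patients may reach the stopping point sooner. Both arms could then show similar CT reduction, with less time or drug in the ultrasound arm. Similar CT reduction would have two readings: no device benefit, or the same result for less exposure. Without infusion time and total tPA beside it, a reader might take the first when the second was true. Conversely, longer infusion in one arm could look like a device effect. At stake is the interpretation of the main result and of the cost argument built on it.

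**Working it through.** **1. What the contrast estimates.** Catheter type is randomized. Stopping time and dose come after randomization and may be consequences of the catheter. Comparing CT reduction by assigned arm at the end of lysis therefore estimates the total effect of assignment, including any effect on how long operators infuse. That is a valid randomized comparison and is what Aim 1 describes. Adjusting for duration or dose would condition on a post-randomization variable, so leaving them out of the analysis of covariance is correct.

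**2. Whether speed goes unmeasured.** Setting the rationale beside the outcomes:

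| Expected consequence (section c) | Where it is measured |
|---|---|
| Shorter ICU stay | Secondary endpoint 1g; cost model |
| Shorter hospital stay | SUMMARY, objective 4 |
| Cost | Aim 4; cost-effectiveness section |

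Bleeding (endpoint 1c) gives some indirect view of drug exposure. Speed itself is not measured, but the consequences that the protocol names for it are.

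**3. How large masking could be.** Inputs from Statistical Analysis: control reduction 43%, ultrasound at least 50% more effective (1.5 × 43 = 64.5%, difference 21.5 points), 40 per arm, power 0.80. The SD and alpha are not stated, so the 40 cannot be reproduced independently. Assuming two-sided 0.05 and a two-sample t-test, the SD that gives power 0.80 is 33.9 points. The normal approximation gives 21.5 / [(1.960 + 0.842) × √(2/40)] = 34.3.

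A further assumption is needed, and it is not in the plan: that 43% and 64.5% apply at equal infusion time. Let f be ultrasound infusion time divided by control time.

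- Exponential clearance: kc = −ln(0.57) = 0.562 and ku = −ln(0.355) = 1.036. Difference = 100 × [1 − exp(−ku × f) − 0.43].
- Linear clearance: difference = 64.5 × f − 43.

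| f | Exponential: points (power) | Linear: points (power) |
|---|---|---|
| 0.90 | 17.6 (0.63) | 15.1 (0.50) |
| 5/6 | 14.8 (0.49) | 10.8 (0.29) |
| 2/3 | 6.9 (0.15) | 0 (0.05) |

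The difference vanishes at f = 0.562/1.036 = 0.54 (exponential) or 43/64.5 = 0.67 (linear).

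Reverse case, identical catheters with one arm infused longer: 10% longer gives 3.1 points (exponential) or 4.3 (linear), significant with probability 0.07 or 0.09. One third longer gives 9.7 or 14.3 points, with probability 0.25 or 0.46. At a constant infusion rate, and reading the cap as a per-patient total, that needs the other arm to have had at most 24/(4/3) = 18 mg.

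**4. What listing the two variables would add.** With 40 per arm, the 95% CI half-width for a difference in means is t(0.975, 78) × √(2/40) = 1.991 × 0.2236 = 0.445 SD. Such intervals would show which exposure differences fit the data. They could not establish equal exposure, and a short infusion can mean either response or complication.

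**The case for a change.** The strongest case for a change is that the remedy costs almost nothing. Start and stop times and total dose are simple procedure data, the rationale invokes speed, and naming these as outcomes in advance would stop their reporting from being optional. The earlier comparisons also looked at exposure: the multicenter registry noted "no difference in outcomes and treatment specifics between USAT and CDT", and the investigators' own series found similar outcomes "with similar procedure length and lytic dose in the time-adjusted cohorts". Neither was randomized, section b warns of selection bias, and this trial could make the same comparison under randomization.

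It stands that the two variables are not listed, and that reporting them by arm would help a reader. It does not stand that the plan yields a wrong answer without them. The same investigators have already treated procedure length and lytic dose as natural things to report, and the 24 mg limit gives a reason to track dose. The documents contain no case report form, and the Schedule of Events lists assessments rather than procedure details, so absence there says little about collection. The remark about similar clearance is rationale, not a decision rule, and binds nobody to conclude that ultrasound has no advantage.

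The masking figures are also weaker than they look. Statistical Analysis gives its effect for the study's thrombus-reduction endpoint and never mentions equal time. If the planned effect already reflects operator stopping, the loss of power does not arise. Stopping is guided by clinical, hemodynamic or echocardiographic change, not CT, so CT clearance need not follow infusion time as either model supposes.

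**Conclusion.** No change is called for. The primary comparison is a valid randomized estimate of the total effect of catheter assignment under operator-chosen stopping, and it agrees with Aim 1. Free dosing and stopping is a fair pragmatic choice in a trial that describes both treatments as standard of care.

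What remains is a reporting gap: infusion duration and total tPA are not named, so similar CT reduction could be set against time and drug use only through ICU stay, hospital stay, bleeding and costs. Analysts can fill that gap by tabulating both by arm with confidence intervals beside the primary result, as outcomes and not as covariates. With a half-width of about 0.45 SD, those intervals would inform the interpretation without settling it.

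The size of any masking is unknown. The illustration runs from a modest loss (17.6 or 15.1 of 21.5 points at 10% shorter infusion) to complete masking at 54% to 67% of control time. It rests on an equal-time effect, a back-solved SD of 33.9, two-sided 0.05 and a clearance model, none of which the documents supply.

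### Recurrent VTE (item 1d) requires a new defect for PE but only a positive compression ultrasound for DVT, so residual index thrombus in a symptomatic patient could be counted as a recurrence

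*Combined protocol and SAP*

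**What the plan says.** The endpoint is item 1d under Secondary Endpoints in section d (Approach) of the combined protocol and SAP: "Recurrent venous thromboembolism (VTE) during 90-day follow-up". The rule has a clinical condition and an imaging condition: "Recurrent VTE will be diagnosed if suspected symptoms or signs of deep vein thrombosis or acute PE are objectively confirmed by an imaging test".

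The accepted imaging results follow in brackets. For PE they are a "new filling defect by pulmonary angiography or contrast-enhanced chest CT, new high-probability perfusion defect revealed by lung scan". For DVT the result is a "positive compression ultrasound study for deep vein thrombosis". The same item adds: "There will be no routine surveillance for asymptomatic recurrent VTE".

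The tests required of every patient at baseline, listed in section d, are a chest CT angiogram ("Chest CT angiogram with contrast diagnostic of PE"), a transthoracic echocardiogram and cardiac biomarkers. The table headed "Schedule of Events" repeats these and adds a second chest CTA within 48 hours after lysis. Neither place lists a venous ultrasound at any visit.

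**The concern.** In a population that all enters with acute thromboembolism, newness is what separates a recurrence from the index disease. Item 1d applies that test to the lungs and omits it for the veins. A patient may enter with DVT as well as PE, and a vein may still be non-compressible when that patient is scanned for symptoms during the following 90 days. Read literally, the rule makes that scan a recurrence.

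What is at stake is a reported safety and efficacy rate. Recurrences are likely to be few with 40 patients per arm, so one or two misclassified events can change the reported figure noticeably. False events at the same rate in both arms also pull a risk ratio towards 1. They could reach the cost-effectiveness model, which takes its point estimates from the trial data and includes adverse-event costs. That last step is an inference: the plan does not name recurrent VTE as a model input, and it does not say whether the major adverse events of item 1e include it.

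**Working it through.** The plan gives no recurrence rate, DVT prevalence, significance level or power for this endpoint, so there is no stated figure to reproduce. The finding rests on comparing the text; the arithmetic only illustrates scale.

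**Step 1. The imaging criteria side by side (item 1d, baseline list, Schedule of Events).**

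| Result accepted | Must be new? | Comparator scheduled by the plan? |
|---|---|---|
| Filling defect, pulmonary angiography or chest CT | Yes | Yes: chest CTA at baseline and within 48 hours after lysis |
| High-probability perfusion defect, lung scan | Yes | No earlier lung scan, but newness is required |
| Compression ultrasound for DVT | No | No venous ultrasound at any time |

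The ultrasound criterion is the only one of the three with neither the qualifier nor a scheduled comparator.

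**Step 2. Who can be misclassified.** The clinical condition is symptoms or signs of DVT *or* of acute PE, and the text does not tie either presentation to a particular imaging result. Two kinds of patient with only residual thrombus can meet the rule:
- one with persisting limb symptoms and a positive scan;
- one with suspected PE whose work-up includes a positive venous scan.

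A patient without symptoms or signs does not meet it.

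**Step 3. Is the gap closed elsewhere?** Two blinded independent readers are named for the CTAs and two for the echocardiograms. The plan describes no adjudication of VTE events and no rule for separating residual from new venous thrombus.

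**Step 4. Scale, on assumptions not in the documents.** Let r be the proportion of patients with residual DVT and s the proportion of those scanned for symptoms within 90 days. The arm size of 40 comes from the Statistical Analysis section.

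False events per arm = 40 × r × s

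| r | s = 5% | s = 10% | s = 20% |
|---|---|---|---|
| 20% | 0.4 | 0.8 | 1.6 |
| 40% | 0.8 | 1.6 | 3.2 |
| 60% | 1.2 | 2.4 | 4.8 |

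Over both arms the range doubles to 0.8 to 9.6. With s = 0 it is 0.

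**Step 5. Effect on a comparison, again on assumed rates.** Take true risks p of 2% and 6% and a false-positive rate f equal in both arms.

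Observed risk = p + (1 − p) × f

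| f | Observed risks | Risk ratio | Difference (points) |
|---|---|---|---|
| 0 | 2.00% vs 6.00% | 3.00 | 4.00 |
| 2% | 3.96% vs 7.88% | 1.99 | 3.92 |
| 5% | 6.90% vs 10.70% | 1.55 | 3.80 |
| 10% | 11.80% vs 15.40% | 1.31 | 3.60 |

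For f = 5%: 0.02 + 0.98 × 0.05 = 0.069; 0.06 + 0.94 × 0.05 = 0.107; 0.107 / 0.069 = 1.55. The difference is (1 − f) × 4 points, so it shrinks by only 2% to 10% of its value. The risk ratio falls mainly because both risks rise.

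**Step 6. Power.** With 40 per arm and a two-sided Fisher exact test at an assumed level of 0.05, power for 2% against 6% is about 1.5% with perfect classification, and about 2% to 4% at the false-positive rates above. The trial could not detect such a difference under either wording.

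**The case against.** The strongest objection is that the rule is narrower than the ultrasound phrase suggests. A reader who takes that phrase alone might infer that any positive scan counts, and that residual DVT will routinely be recorded as recurrence. The documents do not support this. The same sentence requires suspected symptoms or signs, and item 1d rules out surveillance for asymptomatic recurrence, so silent or incidental residual thrombus does not qualify. This stands, and it limits the finding to symptomatic patients who are scanned. It does not remove it, because such a patient still meets the rule.

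It can also be said that the item is headed as recurrent VTE, and that a sensible investigator would not call known, unchanged thrombus a recurrence. That is a fair reading of the intent. But with no earlier scan required, the investigator may have no means of knowing that the thrombus is unchanged, and the plan gives no instruction for that case.

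A reader might further infer that the gap biases the treatment comparison in a way that matters. The documents do not support this either. The rule is the same in both arms, the endpoint is secondary, and the study is powered only on the CT obstruction index: "We estimated a sample size of 40 per group to detect the differences with a power of 0.80". Under the assumed rates the absolute difference hardly moves and power is negligible with or without the error. The risk ratios are arithmetically correct but rest on invented rates, and nothing in the documents shows that the 10% case is plausible. What survives is an inflated and noisier recurrence rate.

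**Conclusion.** The point holds as a gap in one criterion of one secondary endpoint: followed literally, item 1d could count residual index thrombus as a recurrence in a patient with symptoms or signs of DVT or PE. The consequence is a recurrence rate that may be too high in both arms, and possibly in whatever cost inputs are drawn from it. The primary endpoint and the sample size are not touched.

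The textual finding needs no numerical assumption. Its size cannot be derived from the documents. The 0.4 to 4.8 false events per arm depend wholly on the assumed 20% to 60% with residual DVT and 5% to 20% of those scanned for symptoms, and should be read as a range of possibilities. The correction is worth making because a reported event rate depends on it and it costs little.

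**What to change.** Reword the DVT part of item 1d to require compression ultrasound showing a new non-compressible venous segment compared with an earlier study, where one exists. Where a symptomatic patient has a positive scan and no earlier study, record the event as DVT, new versus residual undetermined. Report the 90-day recurrence count by arm twice, with and without the undetermined events.

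Both counts are needed. Leaving every event without an earlier scan out of a single main count would discard true new DVTs and replace possible over-counting with possible under-counting.

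The cost is one sentence in the endpoint definition, one category on the event form and one extra line in the results table. No scan is added. The downside is that, because the plan requires no baseline venous scan and does not say that any is done routinely, a sizeable share of DVT events may be undetermined. The two counts may then lie well apart, and neither should be presented alone as the true rate.
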